1.3 Inclusion criteria

- 1) Paroxysm pain involving branches of the 2nd and/or 3rd branch of trigeminal nerve.
- 2) The visual analogue score(VAS) baseline score ≥ 5 points, have a attack more than 3 times a day, at least 4 days a week.
- 3) 18 years \leq age \leq 80 years.
- 4) Clear consciousness, have the ability of pain perception and resolution, can complete the basic communication.
- 5) Signed informed consent and volunteered to participate in this study.

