1.7 Termination criteria

- 1) A diagnostic physician at each center will assess the severity of the disease in the study. If the subjects showed the symptoms of facial pain that could not be alleviated by acupuncture (the VAS score > 8 points), the physician will assess the seriousness and terminate the study.
- 2) During the study period, the subjects had serious adverse events such as severe infection, coma, shock, even death and so on, the main investigator should be reported immediately and the study should be terminated immediately.

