2.1 Sample size estimation

The glmpower process of SAS9.3 software is applied to estimate the sample size. According to the literature and the preliminary experiment, the mean values of the

VAS score of EA+Carbamazepine group, EA+Placebo group, sham EA+Carbamazepine group, sham EA+Placebo group were 5.23,4.45,5.50,0.00. The standard deviation was 1.6. Under the condition of $\alpha=0.05$, the test efficiency $1-\beta=0.8$, the four groups were allocated with the 1:1:1:1 proportion, the sample size of each group was calculated at least 24. Considering the existence of shedding and other factors, in the premise of guaranteeing the minimum sample size, the sample size was enlarged by 20% to 30 cases in one group, in total 120 cases for 4 groups. Because of the complexity of the sample calculation process of factorial design, the formula is not listed here.

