after acupuncture, which refers to the duration of acupuncture 1 hours and above, appear the needle pain, nausea, vomiting, palpitations, dizziness, headache, anorexia and insomnia and other symptoms. Each time the patient is diagnosed and treated, ask if any of the above situations occur. If so, record it immediately.

2) Adverse reaction of carbamazepine:

Blurred or diplopia vision, drowsiness, weakness, nausea, vomiting, mental and/or neurological abnormalities and others.

3) Acupuncture expectation evaluation:

The evaluation is divided to "would be (1 point), not to be (-1 point), not clear (0 point)" to answer the curative effect of acupuncture treatment of CTN and other diseases. Time points: before acupuncture treatment, after acupuncture treatment, follow-up period.

(5) The evaluation of blindness

The subjects will be asked to accept true acupuncture, sham acupuncture or uncertainty. Researchers will compare the percentages of the two groups.

Evaluation time: at the end of the 4th week of any acupuncture treatment.

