2.8 Measures to improve the compliance of subjects

The compliance of patients was measured by the number of treatments. The calculation formula is as follows:

Criteria are the number of treatments that the subject has received over 80 percent of the treatment (including 80%).

In order to obtain a better compliance and make the final summation of the patient is not less than 80% of the total number of cases in the trial, so the following measures are adopted to improve patient compliance: Adhere to the principle of voluntary, sign the patient informed consent; We will improve and maintain the patient's compliance with the medical quality, the medical treatment environment, the medical expenses, etc., and encourage patients to persist in treatment during the study period; Provide the patient with a certain amount of transportation expenses and labor costs; Pay attention to the establishment of a good doctor-patient relationship, explain the purpose and necessity of the examination, treatment and review to the included cases, and obtain the consent and cooperation of the patients . Record the patient's contact information in detail for follow-up.

[figure not shown]
Part3. The key technology

1. The establishment of an effective treatment program of EA therapy for CTN is the first key technology in the study. The therapy technologies including acupoints selection, needling technique, EA parameters selection, needle retaining time, treatment frequency and how to apply acupuncture combined with carbamazepine.

2. The study design and the quality control of the clinical study is another key technique in this project. Grasping the above key technologies will help to develop a scientific and standardized research program at home and abroad, which can provide a

higher level of evidence-based medical evidence for the clinical effect of CTN by EA therapy.

Technical Route:

Statistical Analysis Plan

1. Data entry and storage

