2.2 Statistical analysis content

The main analysis contents include:

(1) Four groups of cases distribution: Four groups of the total loss rate and the loss due to adverse events off rate comparison.

(2) Comparability analysis: Compare demographic data and other baseline values to measure the comparability of the four groups.

(3) Compliance analysis: The four groups of patients were compared according to the amount of time to receive the appropriate treatment, the program did not use prohibited drugs.

(4) Effectiveness analysis: Main therapeutic indexes are analyzed by PP and ITT simultaneously. Since this study is a multi-center clinical trial, the effect of the central effect and baseline on the therapeutic effect should be taken into account in the analysis.

(5) Effect factor analysis: such as age, gender, duration, combined medication and other factors on the efficacy.

(6) Safety analysis: First, according to the requirements of adverse reaction correlation list describes four groups of adverse events and adverse reactions (including the number of cases of adverse events and laboratory examination indexes before and after the test "normal turn abnormal cases and different rate), statistical

analysis of the adverse reactions by chi-square test.

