2.3 Statistical analysis method

(1) The measurement data: First of all, the normality test was used. For normal distribution, the t-test, paired t-test, variance analysis and covariance analysis were used to check the data. For non-normal distributions, using rank sum test and paired rank sum test.

(2) The enumeration data: Using the chi-square test, Fisher exact test and so on. The hierarchical data are analyzed by Redit, CMH or other non-parametric tests.

(3) Multi-centers analysis of comprehensive efficacy: The CMH method was used for counting data; Analysis of covariance is used for metering data.

(4) All the statistical tests were double-sided, and the p-value is less than or equal to 0.05 and the difference is statistically significant.

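### The between-arm harm test in SAP 2.2(6) is a crude chi-square that ignores sessions received and time observed, although the protocol's stopping rules can make exposure differ by arm

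*Combined protocol and SAP*

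**What the plan says.** SAP 2.2(6) lists adverse events and reactions for the four groups and then plans "analysis of the adverse reactions by chi-square test". For count data, SAP 2.3(2) offers "Using the chi-square test, Fisher exact test and so on". Neither section mentions sessions, person-time or time to event. Under SAP 2.1, one treatment with a safety record is enough to enter the safety set, and safety data are analysed as available cases.

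Three rules can cut exposure short. Protocol 1.7(1) covers facial pain that acupuncture does not relieve: "the VAS score > 8 points), the physician will assess the seriousness and terminate the study". Protocol 1.5(2) removes patients with obvious adverse reactions, and 1.6(3) counts serious ones as drop-out.

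On collection, protocol 2.6(4) says of needling problems: "Each time the patient is diagnosed and treated, ask if any of the above situations occur". Protocol 2.6 also has a daily diary with an item on side effects of drugs or acupuncture, and it plans safety recording through follow-up. Protocol 2.5 allows emergency carbamazepine, with recording of its use, and does not restrict it by arm.

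**The concern.** A chi-square on patients with a reaction compares like with like only if the arms are watched for similar periods and, for needling events, receive similar numbers of sessions. Here one route to shorter exposure is lack of pain relief, which depends on treatment. A patient terminated early has fewer needle insertions to react to and fewer visits at which the question is put.

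If such patients gather in one arm, the test cannot tell a lower risk from a shorter exposure. Study objective 1 includes the safety of EA, so the comparison at stake is one the trial sets out to make.

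**Working it through.** **Plan's own figure.** The safety section gives no number to reproduce. The inputs below come from elsewhere in the documents or are marked as assumptions.

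**Inputs from the documents.** Twelve sessions over 4 weeks (protocol 2.4). Thirty patients per group (protocol 2.1). Entry requires VAS "baseline score ≥ 5 points", with no upper limit (protocol 1.3). The planning values for EA + carbamazepine, EA + placebo, sham EA + carbamazepine and sham EA + placebo "were 5.23,4.45,5.50,0.00. The standard deviation was 1.6" (protocol 2.1).

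**Assumptions.** The planning means are reductions in VAS. Baseline VAS is normal with mean 6, 7 or 8 and SD 1.6, truncated to 5-10. Change has SD 1.6. Every patient above 8 is stopped. The true 4-week risk R of a needling reaction is 20% or 40%, equal in all arms, with a constant hazard. Nothing is recorded after stopping.

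**Step 1: who exceeds VAS 8.** Take baseline minus change and find the share above 8.

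| Baseline mean | Above 8 at baseline, any arm | Sham EA + placebo (mean change 0.00) | Other arms, full planned benefit | Other arms, a quarter of the benefit |
|---|---|---|---|---|
| 6 | 14% | 25% | under 1% | 9-11% |
| 7 | 27% | 35% | under 1% | 14-17% |
| 8 | 46% | 46% | under 1% | 22-26% |

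The imbalance is strong once the planned benefit is complete and weaker early on, when all arms contain patients who started above 8. Protocol 2.1 gives no time point for its means.

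**Step 2: under-count when a share q stops after week t.** The risk accrued by week t is r(t) = 1 − (1 − R)^(t/4). The observed proportion is (1 − q)R + q·r(t), so the under-count is q(R − r(t)). With q = 0.30 in sham EA + placebo and no stopping elsewhere:

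| Stop after | R = 20%: r(t), observed, under-count | R = 40%: r(t), observed, under-count |
|---|---|---|
| Week 1 | 5.4%, 15.6%, 4.4 points | 12.0%, 31.6%, 8.4 points |
| Week 2 | 10.6%, 17.2%, 2.8 points | 22.5%, 34.8%, 5.2 points |
| Week 3 | 15.4%, 18.6%, 1.4 points | 31.8%, 37.5%, 2.5 points |

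At 30 patients, 8.4 points is about 2.5 patients with an event (30 × 0.084).

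**Step 3: stopping in other arms too.** Suppose that 35% of sham EA + placebo and 15% of the comparison arm stop after week 1. The false difference is (0.35 − 0.15)(R − r(1)). For R = 20% this is 0.20 × (0.200 − 0.054) = 2.9 points. For R = 40% it is 0.20 × (0.400 − 0.120) = 5.6 points.

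**Step 4: effect on the test.** With no true difference, 30 against 30, stopping at the halfway point in 10-50% of one arm and true risks of 10-40%, the uncorrected two-sided chi-square rejects in 5.0-10.4% of trials. With equal observation it rejects in 4.9-5.4%.

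**Step 5: carbamazepine reactions.** Assume reaction risks of 10% off and 30% on carbamazepine, with 30% of sham EA + placebo stopped after week 1. Here r(1) = 1 − 0.9^(1/4) = 2.6%, so the under-count is 0.30 × (0.100 − 0.026) = 2.2 points. Rescue use by 0.022 / (0.30 − 0.10) = 11% of that arm would cancel it. With halfway stopping of 10-50% and risks of 10-20% off and 30-40% on drug, the cancelling share runs from 2% to 24%.

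**The case against.** A reader might infer that the rule bites almost only in sham EA + placebo, so that both EA and carbamazepine will look more harmful than they are, by about 8 points. The documents do not support that much.

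- **Rescue.** Patients with unrelieved pain are also the likeliest to take emergency carbamazepine. Their drug reactions then count in the control arm and pull the other way. This stands for drug reactions. It does not touch needling events, which tablets cannot cause.
- **Recording.** Protocol 1.7(1) does not define termination as the end of observation, safety recording is planned through follow-up, and the diary does not depend on treatment visits. This stands as a reason to treat the losses as upper figures. But no section requires contact after termination, and the number of needling sessions falls whatever is recorded later.
- **Planning means.** Protocol 2.1 words them as VAS scores. Read that way, the order reverses: about 0% above 8 in sham EA + placebo and 1.3-5.9% elsewhere. Reductions are the more coherent reading, since patients enter at 5 or more and double placebo would otherwise abolish pain, but it remains an assumption.
- **Timing.** The 8-point figure pairs stopping after week 1 with full benefit in the other arms by then. With partial benefit the gap is nearer 3-6 points, and late stopping costs only 1-3.
- **Active arms.** Removal for a drug reaction ends needling observation too. The triggering reaction is counted, but later reactions of the other type are not.
- **Factorial comparison.** If EA is compared over both drug levels, only half the reference patients are sham EA + placebo, so the bias roughly halves.
- **Existing safeguards.** SAP 2.2(1) and (3) compare loss and treatment received by group. That would make unequal exposure visible, but neither feeds into the harm test.

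**Conclusion.** The plan's only between-arm harm tests are crude comparisons of proportions, while its own stopping rules can make sessions and observation time unequal. That much rests on the text alone.

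A direction can be stated only for needling reactions, and only if the planning means are reductions: sham EA + placebo would be under-counted and EA would look somewhat more harmful. On the assumptions shown, the size is about 4-8, 3-5 or 1-3 points for stopping after week 1, 2 or 3. It is smaller if other arms also stop early, if the physician does not stop every patient above 8, or if the diary captures later events. For carbamazepine reactions the net direction is undetermined. The distortion falls mainly on the estimate, and the false-positive rate rises only modestly in most cases. The change is worth making because it is cheap and the data it needs are largely collected already.

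**What to change.** In SAP 2.2(6), keep the crude proportions by arm as description and make the between-arm comparison exposure-based:

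- **Needling events:** events per session delivered, by Poisson or negative binomial regression with log sessions as offset, or an exact rate comparison if events are sparse.
- **Other reactions:** time to first reaction (Kaplan-Meier, log-rank), or events per patient-week observed.
- **Reporting:** sessions received, weeks observed and rescue carbamazepine use, by arm.
- **Collection:** state in the protocol that adverse events in patients who stop early are still collected, by diary or phone, to the scheduled end of week 4, and that they count in the allocated arm.

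The cost is SAP wording, one extra model, a few phone contacts, and rates that readers know less well than percentages. Session counts need no new collection, since protocol 2.8 already says "The compliance of patients was measured by the number of treatments". No change to the termination threshold, treatment or rescue is proposed.

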2.3 Statistical analysis method

(1) The measurement data: First of all, the normality test was used. For normal distribution, the t-test, paired t-test, variance analysis and covariance analysis were used to check the data. For non-normal distributions, using rank sum test and paired rank sum test.

(2) The enumeration data: Using the chi-square test, Fisher exact test and so on. The hierarchical data are analyzed by Redit, CMH or other non-parametric tests.

(3) Multi-centers analysis of comprehensive efficacy: The CMH method was used for counting data; Analysis of covariance is used for metering data.

(4) All the statistical tests were double-sided, and the p-value is less than or equal to 0.05 and the difference is statistically significant.

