ID: 2018ZY008-CTN

Research name:

*Electroacupuncture Therapy for Change of Pain in
Classical Trigeminal Neuralgia*

Date: June 20, 2018

Electroacupuncture Therapy for Change of Pain in Classical Trigeminal Neuralgia

Study Protocol

Part1. Study objectives

1. To observe the therapeutic effect and safety of electroacupuncture (EA) in the treatment of classical trigeminal neuralgia (CTN).
2. To evaluate whether EA has the advantage over carbamazepine in the immediate effect, long-term effect and post effect of the analgesia in CTN.
3. To demonstrate whether EA has a synergistic effect with carbamazepine on the treatment of CTN, or even whether EA has an alternative effect on carbamazepine.
4. To establish a standardized, effective and convenient therapy program of EA to promote it widely.

Part2. Study program

1. Study subjects

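### The SAP does not fix the test or the contrast for the main VAS outcome: a normality switch can drop the required adjustment, and no interaction, EA-versus-carbamazepine or primary contrast is named

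*Combined protocol and SAP*

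**What the plan says.** Objective 2 (protocol Part 1) is "To evaluate whether EA has the advantage over carbamazepine in the immediate effect, long-term effect and post effect of the analgesia in CTN". Objective 3 begins "To demonstrate whether EA has a synergistic effect with carbamazepine on the treatment of CTN" and goes on to ask whether EA could serve as an alternative to carbamazepine.

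SAP 2.3(1) covers all measurement data and starts with a normality test. One branch reads "For normal distribution, the t-test, paired t-test, variance analysis and covariance analysis were used to check the data", the other "For non-normal distributions, using rank sum test and paired rank sum test". SAP 2.3(3), on combined efficacy across centres, says "Analysis of covariance is used for metering data". SAP 2.2(4), which is specific to the main therapeutic indexes, says "the effect of the central effect and baseline on the therapeutic effect should be taken into account in the analysis", and has those indexes analysed in the PP and ITT sets together. SAP 2.3(4) sets the significance rule: "All the statistical tests were double-sided, and the p-value is less than or equal to 0.05".

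The SAP refers only to four groups. A factorial design is mentioned in protocol 2.1 alone, which gives the planning values ("sham EA+Placebo group were 5.23,4.45,5.50,0.00. The standard deviation was 1.6") but not the effect that was powered.

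**The concern.** Two things are left open for the main outcome.

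- **The test.** Read literally, 2.3(1) sends non-normal VAS data to rank-sum tests. These have no baseline or centre term, so they conflict with 2.2(4). They compare groups and cannot test an EA x carbamazepine interaction. The normal branch does not choose between an unadjusted t-test and ANCOVA.
- **The contrast.** Even if 2.3(3) governs, an ANCOVA could be a single four-group test. Nothing names the interaction (synergy, objective 3), EA+placebo versus sham EA+carbamazepine (objective 2), or which contrast is primary.

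At stake is which result answers each objective, whether it is adjusted, and how many tests at 0.05 may be called positive.

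**Working it through.** **Inputs (protocol 2.1).** Means 5.23 (EA+carbamazepine), 4.45 (EA+placebo), 5.50 (sham EA+carbamazepine), 0.00 (sham EA+placebo); SD 1.6; alpha 0.05; power 0.80; 24 per group, enlarged to 30. Two-sided testing is from SAP 2.3(4).

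**Formula.** For a contrast L = sum of c x mean, noncentrality = L / (1.6 x sqrt(sum of c² / n)), with 4n - 4 error df and the noncentral t distribution.

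**Step 1: reproduce 24 per group.**

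| Contrast | Value | n per group for 80% |
|---|---|---|
| EA main effect | (5.23 + 4.45)/2 - (5.50 + 0.00)/2 = 2.09 | 6 |
| Carbamazepine main effect | (5.23 + 5.50)/2 - (4.45 + 0.00)/2 = 3.14 | 3 |
| Interaction | 5.23 - 4.45 - 5.50 + 0.00 = -4.72 | 5 |
| EA+placebo v sham EA+carbamazepine | 4.45 - 5.50 = -1.05 | 37 |
| EA+carbamazepine v EA+placebo | 0.78 | 67 |
| EA+carbamazepine v sham EA+carbamazepine | -0.27 | 552 |
| EA+placebo v sham EA+placebo | 4.45 | 3 |
| Overall four-group test | 3 df | 3 |

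No unadjusted contrast gives 24 per group. As a total, 24 does fit: the EA main effect needs 6 x 4 = 24 (power 0.86; 5 per group gives 0.78). The enlargement reproduces: 24/(1 - 0.20) = 30.

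**Step 2: power at 30 per group.** Main effects and interaction exceed 99%. Head-to-head, unadjusted: 1.05/(1.6 x sqrt(2/30)) = 2.54 on 116 df, power 0.712 (0.614 at 24 per group). Rank-sum on normal data, by simulation: 0.676.

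**Step 3: head-to-head with ANCOVA.** The baseline correlation r is not in the documents, so 0.3-0.7 is assumed. The error variance is multiplied by 1 - r² if 1.6 is the SD of the score, or by (1 + r)/2 if it is the SD of change (equal SDs at both visits assumed).

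| r | 1.6 = SD of score | 1.6 = SD of change |
|---|---|---|
| 0.3 | 0.752 | 0.878 |
| 0.5 | 0.829 | 0.829 |
| 0.7 | 0.942 | 0.780 |

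**Step 4: how much is due to the switch.** Assume Shapiro-Wilk at 0.05 in each arm, any rejection leading to rank-sum and otherwise ANCOVA. On normal data with r = 0.5, the switch occurs in 19% of trials. Power is 0.797 against 0.823 for always-ANCOVA at 30 per group, and 0.705 against 0.732 at 24. On assumed bounded scores (baseline mean 6.5, SD 1.2, kept to 5-10; end mean 3.5, SD 2, clipped to 0-10; r = 0.4; 10-30% pain-free), switching changes power by -0.8 to +0.3 points, and ANCOVA gains only 1.0 to 1.6 points over the t-test.

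**Step 5: direction.** If the means are reductions (assumed; as scores, sham EA+placebo at 0.00 would be pain-free), EA adds 4.45 - 0.00 = 4.45 without carbamazepine and 5.23 - 5.50 = -0.27 with it. The pooled effect, (4.45 - 0.27)/2 = 2.09, describes neither stratum. The head-to-head difference then favours carbamazepine, and the chance of significance in EA's favour at 30 per group is about 0.0004%.

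**Step 6: false positives.** The interaction and head-to-head contrasts are uncorrelated in a balanced design: 1 - 0.95² = 0.0975 for at least one false positive at one visit. Simulation with the shared error variance gave 0.094.

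**The case against.** The strongest defence is that adjustment is already dealt with. Section 2.2(4) is specific to the main indexes and requires centre and baseline, and 2.3(3) assigns ANCOVA to measurement data. Section 2.3(1) can be read as a general toolkit, since its paired tests cannot be between-arm efficacy tests. That reading is reasonable, but no sentence gives 2.3(3) precedence over the normality rule, and it leaves the missing contrast untouched.

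Several stronger readings are tempting, and the documents do not support them:

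- **The objectives are untestable.** The ANOVA and ANCOVA listed could carry both contrasts. They are unspecified, not impossible.
- **The normality switch seriously costs power.** It costs about 3 points or less, and the adjustment gain may be only 1-2 points on bounded scores.
- **The sample size gives no clue to its target.** A total of 24 fits the EA main effect exactly, so a total may have been reported as per group. That is an inference from arithmetic; protocol 2.1 states 24 for each group.
- **The 71% is power to show an EA advantage.** If the means are reductions, it is power to detect a difference that favours carbamazepine.
- **The planning means defeat objective 3.** A less-than-additive pattern does not support synergy, but it is compatible with the objective's second half, on EA as an alternative.
- **False positives reach 25-32%.** That requires both contrasts at all four post-baseline visits. Protocol 2.6 sets the first main outcome at 6 months, where the figure is 9-10%.

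**Conclusion.** The concern holds as a gap in prespecification that should be closed before analysis. The SAP states a rule that, if followed for VAS, contradicts 2.2(4) and cannot address synergy. It names neither the interaction nor the head-to-head contrast, gives no primary contrast, and applies 0.05 to every test.

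The choice of contrast has the larger effect: over 99% power for the factorial effects against about 71% for the unadjusted head-to-head difference at 30 per group. Adjustment could move that 71% to 75-94% or 88-78%, depending on which SD 1.6 represents and on assumed correlations, or hardly at all on bounded scores. These figures use the full 30 per group, with no allowance for dropout. The remarks on direction and additivity rest on reading the means as reductions, which protocol 2.1 does not state. Confidence is high in the omission and lower in the size of its consequences.

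**What to change.** - State that the normality switch and the unadjusted tests in 2.3(1) do not apply to the main outcome.
- Analyse change in 2-week mean VAS at 6 months with one ANCOVA: EA (yes/no), carbamazepine (yes/no), EA x carbamazepine, baseline VAS and centre.
- Report the interaction, the EA+placebo versus sham EA+carbamazepine contrast, the four cell means and the simple effects, all with 95% CIs. Interpret pooled main effects only in the light of the interaction. Say which estimate addresses the second half of objective 3.
- Name one primary contrast or a test order, and the primary analysis set. Treat other contrasts and time points as secondary, and say where the second main index stands.
- Keep rank-based analyses as sensitivity analyses.
- In protocol 2.1, say which effect was powered, whether the means are scores or reductions, and whether 24 is a total or a per-group figure.

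The cost is a few sentences and one PROC GLM or MIXED call with ESTIMATE statements. No further data and no patient burden are involved.

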2.6 Therapeutic effects indexes

Subjects are required to write a verifiable diary card to record their pain symptoms in 24 hours every day. The diary includes the following items: (1) daily attack frequency (spontaneous and provoking pain frequency); (2) provoking factors; (3) average pain intensity(VAS) in the past 24 hours; (4) side effect in the past 24 hours (including side effect of drugs or acupuncture); (5) Is there another analgesia therapies have been adopt ? Please record it.

(1) Indexes of main outcome evaluation

- 1) Change from Baseline Intensity of Pain at 6 months (evaluation of the pain by VAS with 0-10 points).
- 2) Change from Baseline Brief introduction of 2-week pain.

Evaluation method: According to pain diary, we will take average data of 2 weeks before treatment (-2~0 week) as baseline, 2 weeks of treatment phase (1~2 week) as data of treatment phase I, 4 weeks of treatment phase (3~4 week) as data of treatment phase II. During the follow-up period, the pain diary card will be continued in the 2 weeks before 3 months (11~12 week)/6 months (23~24 week) after treatments.

(2) Indexes of secondary outcome evaluation

- 1) Brief Pain Inventory-Facial scale (BPI-Facial)
- 2) Patient Global Impression of Change (PGIC)
- 3) Short-Form McGill Pain Questionnaire
- 4) Short- Form 36 Questionnaire

(3) Research cycle and evaluation time points

The treatment periods of this research are 4 weeks, and the follow-up period is 6 months. The above indexes are observed at the time points of baseline (the same day with the grouping and treatment for the subject), treatment period I (the end of the 2nd week), treatment period II (the end of the 4th week), follow-up period I (3rd months after treatment) and follow-up period II (6th months after treatment). The main outcome indexes will be measured weekly (1th week to 4th weeks) during the treatment period.

(4) Safety evaluation and acupuncture expectation evaluation

The relevant safety indicators during the treatment period and during the follow-up period are recorded at any time on the subjects' adverse event records, which is recorded by the acupuncture physician.

- 1) Safety evaluation of electric needle:

The abnormal acupuncture should be record, including broken needle, left needle, fainting, unbearable acupuncture pain (VAS \geq 8 points), local hematoma, infection and abscess. And the symptoms, average degree and average duration of other discomfort

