2.1 Analysis data set

(1) Full Analysis Set (FAS):

A collection of all randomly assigned and at least one treated case. When analyzing the main therapeutic indicators, the missing values in the FAS set were

transferred to the current (LOCF) method by using the results observed at the latest time point. The Available Case Analysis principle was used in the Analysis of secondary efficacy indicators, general conditions and safety Analysis.

(2) Per Protocol Set (PPS):

Compliance set refers to meet the inclusion criteria and follow the test protocol to complete the treatment of the set of cases, which is consistent with the test protocol, compliance, did not take prohibited drugs, to complete the evaluation of effectiveness (at least the main outcome) cases.

(3) Security Analysis System (SAS):

At least one treatment is received and the actual data of the safety indicator evaluation record is available.

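### Two unranked main outcomes, the second undefined, with no primary analysis set and no multiplicity rule: 5% is not secured even for one contrast

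*Combined protocol and SAP*

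**What the plan says.** **Outcomes.** Protocol section 2.6 (1) gives two numbered main outcomes: "Change from Baseline Intensity of Pain at 6 months", measured by VAS, and "Change from Baseline Brief introduction of 2-week pain". Neither is ranked. The evaluation method below them describes diary averages over several two-week windows (weeks 1–2, 3–4, 11–12 and 23–24) and does not tie the second outcome to any of them.

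**Analysis sets.** SAP section 2.2 (4) states: "Main therapeutic indexes are analyzed by PP and ITT simultaneously". SAP section 2.1 defines an FAS and a PPS but not an ITT set. The FAS is "A collection of all randomly assigned and at least one treated case", with missing main-outcome values "transferred to the current (LOCF) method by using the results observed at the latest time point".

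**Decision rule.** SAP section 2.3 (4) states: "All the statistical tests were double-sided, and the p-value is less than or equal to 0.05 and the difference is statistically significant". Nothing in the protocol or SAP orders the tests, splits alpha, requires both outcomes to succeed, or names the contrast among the four arms that carries the 5%. The sample size (protocol section 2.1) uses alpha 0.05 once.

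**Related rules.** Protocol section 1.5 keeps removed cases out of the efficacy analysis. Protocol section 1.6 says that data of shed cases are not to be carried forward in follow-up. For the main outcome, protocol section 2.6 (1) says "we will take average data of 2 weeks before treatment (-2~0 week) as baseline", while 2.6 (3) places the baseline visit on the day of grouping.

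**The concern.** A confirmatory trial needs to say in advance which result, in which patients, decides it. Here two outcomes, two analysis sets and several factorial contrasts are each open to a 0.05 test, and nothing says which one the conclusion rests on. If success may be claimed on whichever main outcome crosses 0.05, the 5% used for the sample size is not held.

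The undefined second outcome makes this worse. With no stated measure or time point, it could be settled after the data are seen.

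The conflicts over who enters the efficacy analysis, and over carrying data forward, fall on the same 6-month result. Two analysts who followed this plan could use different patients and different imputed values. These conflicts are definition gaps and do not enter the error rates below.

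**Working it through.** **1. The plan's own figure.** Inputs from protocol section 2.1: means 5.23 (EA+carbamazepine), 4.45 (EA+placebo), 5.50 (sham EA+carbamazepine) and 0.00 (sham EA+placebo); SD 1.6; alpha 0.05; power 0.80; stated result 24 per group. For a contrast with weights c, the noncentral F parameter is n(Σcμ)² / (1.6² Σc²) with 1 and 4(n − 1) df. The smallest n per group with at least 80% power is:

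| Test | Difference | n per group |
|---|---|---|
| Overall, four groups | – | 3 |
| EA main effect: 4.84 − 2.75 | 2.09 | 6 |
| Carbamazepine main effect: 5.365 − 2.225 | 3.14 | 3 |
| Interaction: 5.23 − 4.45 − 5.50 + 0.00 | −4.72 | 5 |
| Each other arm vs sham EA+placebo | 4.45 to 5.50 | 3 |
| EA+placebo vs sham EA+carbamazepine | −1.05 | 37 |
| EA+carbamazepine vs EA+placebo | 0.78 | 67 |
| EA+carbamazepine vs sham EA+carbamazepine | −0.27 | 552 |

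None gives 24, so the sample size does not reveal which contrast was meant as primary. The dropout step does reproduce: 24 / (1 − 0.20) = 30.

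**2. Either of two outcomes, one contrast, one set.** Each test is two-sided at 0.05, there is no true effect, and the test statistics Z₁ and Z₂ are bivariate normal with correlation r. The documents give no r, so it is an assumption.

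Error = 1 − P(|Z₁| ≤ 1.96 and |Z₂| ≤ 1.96). At r = 0 this is 1 − 0.95² = 9.75%.

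| r | 0 | 0.5 | 0.8 | 0.9 | 0.99 | 1 |
|---|---|---|---|---|---|---|
| Error | 9.75% | 9.1% | 7.8% | 7.0% | 5.7% | 5% |

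With no assumption on the joint distribution the bound is 0.05 + 0.05 = 10%. If both outcomes had to succeed, the error could not exceed 5%.

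**3. One outcome, either analysis set.** This further assumes that a win in either set counts, that ITT means the FAS, and that the PPS is a subset chosen independently of outcome. The two test statistics then correlate at √(PPS/FAS). The ratio is also assumed.

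| PPS as share of FAS | 90% | 80% | 70% |
|---|---|---|---|
| Test correlation | 0.949 | 0.894 | 0.837 |
| Error | 6.5% | 7.1% | 7.6% |

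**4. Related rules side by side.**
- Protocol section 1.5 excludes, among others, patients not treated according to their group's plan. The FAS in SAP section 2.1 includes every randomised patient treated at least once. The same patient can be out under one rule and in under the other.
- Protocol section 1.6 bars carrying data forward in follow-up, while SAP section 2.1 applies LOCF to the main outcomes. The first main outcome is at 6 months, in follow-up.
- The diary mean of weeks −2 to 0 can end on the day of grouping. The two baseline statements can therefore both be true.

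**The case against.** The best counter-argument is that the second outcome is a poor translation. The evaluation method beneath it describes one procedure, diary data averaged over two weeks, so it may be the same VAS. In the same window, the inflation nearly vanishes. That stands as a limit on the size. It does not remove the defect, because four post-baseline windows are listed and the diary also records attack frequency, so the text does not identify the outcome.

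Next, VAS at 6 months is listed first and the sample size uses VAS only, which hints at an order. A hint is not a testing order, and protocol section 2.1 gives neither a time point nor a contrast for its means. It is also fair to say that SAP section 2.3 sets a threshold for individual tests and does not define trial success. That is why the error rates are conditional on either outcome counting. Running PP beside ITT is ordinary practice, provided that one is named primary.

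A reader might infer three stronger points that the documents do not support:
- **The error rate is 9.75%.** That needs two uncorrelated outcomes, which is unlikely for two pain measures in the same patients, and an either-wins rule that is not written.
- **The two baseline statements contradict each other.** They can be compatible. The 2.6 (3) statement gives visit times for all the outcomes, including the questionnaires.
- **An alpha split has a known power cost.** The means in protocol section 2.1 cannot carry that figure. They do not reproduce 24, and it is unclear whether they are scores or reductions. The EA main effect is driven by the 0.00: it averages −0.27 (5.23 − 5.50) with carbamazepine and 4.45 (4.45 − 0.00) with placebo.

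**Conclusion.** The concern holds in a limited form. It is certain from the text that the two main outcomes are unranked, that the second is not identifiable, that no analysis set is primary and that no multiplicity rule exists.

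The size is conditional. If either outcome counts, the error for one contrast in one set is about 7% to 9% for assumed correlations of 0.9 to 0.5, nearer 5% if the outcomes almost coincide, and never above 9.75% for jointly normal tests. If a win in either set counted, one outcome alone would give about 6.5% to 7.6% for a PPS of 90% to 70% of the FAS. The 80% target in protocol section 2.8 concerns patients in the final summary and does not fix that ratio.

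The choice among four-arm contrasts is not included, so these figures do not bound the error of the whole trial. The conflicts over removed cases and carried-forward data are real and separate. The point should be corrected; confidence in its size is medium.

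**What to change.** - In protocol section 2.6, name VAS change from baseline to 6 months as the single primary outcome, and state that the diary mean of weeks −2 to 0 is its baseline. The baseline sentence is a clarification.
- In SAP section 2.2, make the FAS the primary set with the PPS supportive, and either define ITT or replace the term with FAS.
- In SAP section 2.3, name one contrast, tied to an objective in Part 1, that carries two-sided 0.05. Label all other tests supportive or exploratory.
- Define the second outcome and its time point, and test it only if the first is significant. Alternatively, keep both with Holm's procedure.
- Reconcile protocol section 1.5 with the FAS in SAP section 2.1 on who enters the efficacy analysis, and protocol section 1.6 with LOCF in SAP section 2.1 on carrying data forward.

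**Cost.** Fixed-order testing is a wording change: no patients are added and the first outcome loses no power. No confirmatory claim on the second outcome is possible if the first fails, and results outside the named tests lose confirmatory status. Holm costs some power because the smaller p-value must reach 0.025. Any power figure from the protocol section 2.1 means should be omitted or marked as illustrative.
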